5.5. Exploratory Subgroup Analyses

In exploratory analyses we will investigate potential differences in treatment effect in subgroups with known or hypothesized risk or protective associations with AD. These are defined in the "Definitions for Subpopulation Analyses" section above.

For each analysis, we will estimate differences in the treatment effect on both the absolute (i.e. risk difference) and relative (i.e. ratio) scales. After calculating the raw differences, we will estimate them based on a model that incorporates the same variables as in other analyses, but with main effects and interactions for the subgroup variables outlined above. Most of these are either binary or continuous; in the case of a multi-level categorical variable, we will use a set of design variables. The analysis addressing ceramides will only use main effects, without interaction terms. The model will use the full ITT dataset with provider-diagnosed AD as the outcome. The p value for the single interaction coefficient (or for the combination of interaction coefficients, if multiple design variables are used) will provide an estimate of statistical significance for a difference in treatment effects in the subgroups being modelled. We plan to use a significance threshold of 0.10 for identifying effects that may warrant further investigation. (Designing the trial for a lower threshold was not feasible.)

More important than p values, we plan to rely on the magnitude of effects to determine whether the intervention is more effective in some subgroups than others. It is difficult to specify a threshold for the magnitude of difference in advance. The planned presentation of results is given in Table 5.

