10.4.2 Effect modification of primary endpoint

We will examine potential modification of the intervention effect by sex (consistent with NIH guidelines), race or ethnicity, atopic family history, climate, and pet ownership by creating separate logistic regression models under multiple imputation that include the variable of interest with intervention status and an interaction term, adjusting for stratification variables. Multiple imputation will be performed as above with the interaction term included in the imputation step. We will test for significance of the interaction term with a two-sided Wald test at the 0.1 level. A level of 0.1 was used because of the exploratory nature of this aim that will be solely used to guide future research and due to the impracticality of fully powering this secondary analysis.

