3.1. Level of Statistical Significance

In the primary analysis, use a type I error rate of 0.05. Secondary outcomes will be considered significant at $\alpha=0.05$ and exploratory analyses at $\alpha=0.1$. All tests will be two-tailed.

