3.3. Confidence Intervals

Estimates will be reported with 95% confidence intervals.

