5.2. Definitions for Subpopulation Analyses

In **exploratory analyses** we will investigate potential differences in treatment effect in subgroups with known or hypothesized risk or protective associations with AD using the approach given in section 5.5 below. The subgroups to be investigated are:

1. **Family history of atopy in a first-degree relative**, associated with approximately doubled risk of AD¹³⁻¹⁶ and expected in 40 to 60 percent of the population, as found in our planning grant and suggested in other studies of IgE sensitization in the population¹⁷. This is one of

our stratification variables for randomization. If the elevated risk in this population is explained by filaggrin gene mutations affecting the skin barrier, then emollient use should be most protective in babies with a family history of atopy; this would point to recommending daily emollient use only in this high-risk population.

We will treat this as a binary variable (*yes* vs *no/don't know*) to the following question:

Has at least one of your baby's blood-related PARENTS, BROTHERS OR SISTERS ever been diagnosed with asthma, eczema (atopic dermatitis) or hay fever (seasonal allergies)?

2. **Dry climate**, which we will measure using the average relative humidity over a year for the clinic's locality in records from the National Climate Data Center and Weather Service. More detailed methods will be developed, following the general approach in previous work, where a protective effect of RR 0.8 was observed in the highest humidity areas¹⁸. If emollient prevents AD by preserving the skin barrier, then the treatment effect should be greatest in low-humidity areas.
3. **Having pets or regular contact with farm animals at baseline**. Meta-analysis has found a protective effect for exposure to dogs (RR 0.72) and pets overall (RR 0.75), with more equivocal evidence for exposure to cats (RR 0.94)¹⁹. We expect about 30% of participants to own cats and 40% to own dogs based on large national pet ownership surveys. This analysis will be conducted in two steps. The first step will use a set of indicator variables for the following yes/no questions, and the second will use an overall binary variable for any regular contact with animals:

Does your baby have regular (at least weekly) contact with farm animals?

Does your family own one or more dogs?

Does your family own one or more cats?

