Table Title	Population	Time Point(s)	Endpoint	Endpoint Type	Summary Statistics by Treatment Assignment
Breathing Problems	ITT	12m,24m	Ever wheeze	Binary(Y/N)	p%(x/n)
			Number of wheeze events over past year (cat)	Count	p%(x/n)
			Wheeze without cold	Binary(Y/N)	p%(x/n)
			Diagnosed asthma	Binary(Y/N)	p%(x/n)
			Asthma predictive index-Y/N (derived)	Binary(Y/N)	p%(x/n)
Allergies	ITT	12m,24m	Skin Prick Test or Blood test	Binary(Y/N)	p%(x/n)
			Food allergy symptoms	Binary(Y/N)	p%(x/n)
			Food exposure	Binary(Y/N)	p%(x/n)
Severity of symptoms and influence on quality of life	AD population	12m,24m	POEM score (0-28)	Continuous	n, mean, SD, Median, min, max
			IDQOL score (0-30)	Continuous	n, mean, SD, Median, min, max
	ITT	12m,24m	Parent-rated health status	Ordinal(1-5)	p%(x/n) n, mean, SD, Median, min, max
			Days of disrupted sleep in the past week	Count(0-7)	p%(x/n) n, mean, SD, Median, min, max
			Adverse reaction to skin product	Binary(Y/N)	p%(x/n)
Adverse events	ITT	12m,24m	Type	Categorical	p%(x/n)
			Ended	Binary(Y/N)	p%(x/n)
			Severity	Categorical	p%(x/n)
			Require HCP visit	Binary(Y/N)	p%(x/n)
			Diagnosis	Categorical	p%(x/n)
			AE Treatment-Y/N	Binary(Y/N)	p%(x/n)
			AE Treatment-name	Categorical	p%(x/n)
			SAE listing	Narrative	n/a
					p%(x/n)
Contact info change	ITT	Any time			p%(x/n)

Table 5. Exploratory analyses

Subgroup	Intervention cumulative incidence	Usual care cumulative incidence	Difference (risk difference) 90% CI	Difference in differences	Risk Ratio 90% CI	Difference (ratio scale)	P value for interaction
Family history of atopy							
Yes							
No							
Climate							
Dry							
Wet							
Domestic animals							
Any							
None							
Cat(s)							
Dog(s)							
Farmanimal(s)							
Sex							
Female							
Male							
Age at randomization							
Youngest							
Middle							
Oldest							
Emollient type used							
CeraVe							
Others							
None							

6. References

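### SAP 5.5 ranks the size of subgroup differences above the interaction test, sets no size threshold, and Table 5 shows no interval on the contrast, so chance differences can be presented as effect modification

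*SAP*

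**What the plan says.** SAP 5.5 fits a model with interaction terms for each exploratory factor and takes the interaction p-value as the measure of significance: "We plan to use a significance threshold of 0.10 for identifying effects that may warrant further investigation". SAP 3.1 adds "All tests will be two-tailed". The next paragraph of 5.5 places effect size above p-values: "we plan to rely on the magnitude of effects to determine whether the intervention is more effective in some subgroups than others". On how large a difference must be, it says "It is difficult to specify a threshold for the magnitude of difference in advance".

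Results go into Table 5 (SAP 5.12). The within-subgroup columns carry intervals, for example "Difference (risk difference) 90% CI", and the risk ratio column is likewise at 90%. The two contrast columns, *Difference in differences* and *Difference (ratio scale)*, show none. An interaction p-value column is present.

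Other sections bear on this:

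- SAP 3.3 sets a general rule: "Estimates will be reported with 95% confidence intervals".
- SAP 5.6 promises 95% intervals on interaction effects for sex, race and ethnicity.
- SAP 3.2 makes no multiplicity adjustment and leaves that to readers.
- SAP 5.2 reasons that if filaggrin mutations explain the excess risk with a family history, emollient should protect those infants most, and "this would point to recommending daily emollient use only in this high-risk population".
- Protocol 10.4.2 justifies the 0.1 level by the "exploratory nature of this aim that will be solely used to guide future research".

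**The concern.** Under 5.5 the test only nominates effects for further work. The judgement that emollient works better in one group than another rests on the observed size of the difference. That size has no pre-stated threshold, and the planned table does not show how precisely it is estimated. A reader of Table 5 would see two subgroup risk ratios, each with its own interval, and a bare difference between them.

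The trial is sized for the overall effect, so subgroup contrasts are imprecise. If contrasts of the size the SAP itself considers arise often by chance, a size-based reading will credit some of them as real. The recommendation wording in SAP 5.2 and the future-research limit in Protocol 10.4.2 also pull in different directions on how a family-history finding would be used.

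**Working it through.** **Inputs.** From SAP 2.3: control incidence 0.24, overall RR 0.70 (0.168), 491 evaluable per arm, 625 enrolled per arm, about 20% loss. From SAP Table 1, as prevalence and AD risk ratio: family history 0.50 and 2.0; high humidity 0.44 and 0.8; cat 0.30 and 1.0; dog 0.37 and 0.7. Its smallest contrast is an RR difference of 0.2. I use N = 1,250 × 0.8 = 1,000 and N = 1,250.

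**1. The plan's own figures.** The standard two-proportion formula (0.24 v 0.168, two-sided 0.05, 80% power) gives 490.5, so 491 per arm, as stated. Table 1's power column did not reproduce. At N = 982, a two-sided 0.10 Wald test on the log ratio of RRs gives, for differences of 0.2/0.3/0.4, family history 0.27/0.45/0.64 against the stated 0.48/0.56/0.64. The SAP gives neither the N nor the full 2×2 tables behind Table 1, so this is a query and not an error. Nothing below uses that column.

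**2. Chance differences, worked for family history at N = 1,000.** Set RR = 0.70 in every infant.

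- Control risk without family history: 0.24 / (0.5 × 2.0 + 0.5) = 0.16. With it: 0.32.
- Intervention risks: 0.112 and 0.224. Each cell holds 250 infants.
- Variance of a log risk is (1 − p)/(np). The sum is 0.0139 + 0.0317 + 0.0085 + 0.0210 = 0.0751, so the SE of the log ratio of RRs is 0.274.
- SD of the RR difference is about 0.70 × 0.274 = 0.192.
- P(difference of 0.2 or more, either way) is about 2 × [1 − Φ(0.2/0.192)] = 0.30. Simulation also gives 0.30.

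**3. All four Table 1 factors, by simulation, with no true effect modification on the RR scale.**

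| N | Factor | ≥0.2 | ≥0.3 | ≥0.4 | Interaction p<0.10 | ≥0.2 but p≥0.10 |
|---|---|---|---|---|---|---|
| 1,000 | Family history | 30% | 13% | 5% | 10% | 20% |
| 1,000 | Humidity | 28% | 11% | 4% | 10% | 18% |
| 1,000 | Cat | 31% | 13% | 5% | 10% | 21% |
| 1,000 | Dog | 32% | 14% | 6% | 10% | 22% |
| 1,250 | Family history | 25% | 9% | 3% | 10% | 15% |
| 1,250 | Humidity | 23% | 8% | 2% | 10% | 13% |
| 1,250 | Cat | 25% | 9% | 3% | 10% | 16% |
| 1,250 | Dog | 27% | 10% | 3% | 10% | 17% |

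The last column counts null trials in which a gap of 0.2 would be visible but the planned test would not flag it. These figures concern the ratio scale only. With a uniform RR the risk differences already differ by family history (0.32 − 0.224 = 0.096 against 0.16 − 0.112 = 0.048).

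**4. What an interval on the contrast would show.** Take observed RRs of 0.84 and 0.64 in a 30/70 split, Table 1's first cat-owner scenario, with control risk 0.24 in both groups. The ratio of RRs is 0.84/0.64 = 1.31. At N = 982 the variance terms are 0.0269 + 0.0160 + 0.0215 + 0.0092 = 0.0736, so SE = 0.271. The 90% interval is 1.3125 × exp(±1.645 × 0.271) = 0.84 to 2.05 (p = 0.32). At N = 1,250 it is 0.88 to 1.95 (p = 0.26). The point estimates alone do not reveal that uncertainty.

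**The case against.** Several points on the other side are sound.

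- **A test is planned.** A reader might infer that the SAP has no threshold at all. It has one, 0.10 on the interaction, and Table 5 shows its p-value. Only the size criterion lacks a threshold.
- **Some contrasts do get intervals.** A reader might infer that none will. SAP 5.6 promises them for sex, race and ethnicity, and SAP 3.3 can be read to cover the rest. The gap is in Table 5's layout.
- **SAP 5.2 is conditional.** A reader might infer a commitment to recommend emollient only for high-risk infants. The sentence explains why the subgroup is of interest if a filaggrin mechanism holds. It is not a decision rule, and the analyses are labelled exploratory throughout.
- **The 0.2 cut-off is not the SAP's,** and the counts above run in both directions. SAP 5.2 states an expected direction for family history. In that direction alone a gap of 0.2 arises in about 16% (N = 1,000) or 14% (N = 1,250) of trials. The interaction test's false flags in that direction fall by about half too, so the comparison is little changed.
- **Preferring effect size to p-values is defensible** where stated interaction power is only 0.36 to 0.65. The 90% level also matches the exploratory alpha of 0.1 in SAP 3.1.

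These points narrow the concern but do not remove it. Section 5.5 still ranks size above the test when deciding whether subgroups differ, and nothing in it ties size to its uncertainty. Low power makes the interval on the contrast more necessary.

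**Conclusion.** The point holds as a defect in the rule as written. Under a uniform RR of 0.7, the smallest contrast in Table 1 appears by chance in 28-32% of trials per factor at N = 1,000 and 23-27% at N = 1,250, roughly two to three times the 10% flagged by the interaction test. Gaps of 0.3 or more appear in 11-14% and 8-10%. Gaps of 0.4 or more appear in 4-6% and 2-3%, so it would be wrong to say that every contrast in Table 1 arises routinely by chance.

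The figures assume the SAP's control risk, the Table 1 prevalences and risk ratios, two-group factors and 1:1 allocation. The 0.2 reference value is Table 1's smallest contrast, not a rule in the plan.

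A reader might go further and infer that a false subgroup claim is almost certain once all planned factors are counted. The documents do not support a figure for that. Prevalences for several factors are not given, age and bathing need not be split in two, and bathing, caesarean birth and ethnicity have no rows in Table 5. Whether the team would over-read a chance difference is also a prediction; the text only permits it. The primary analysis is untouched.

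**What to change.** 1. **SAP 5.5.** Replace the sentence on magnitude with: *A subgroup difference will be judged on the interaction estimate (ratio of RRs and difference in risk differences), with its confidence interval and interaction p-value. Differences between point estimates alone will not be interpreted.* Effect size stays central but is read with its uncertainty.
2. **SAP Table 5.** Add an interval to each of the two contrast columns and use one confidence level throughout, consistent with SAP 3.3 and 5.6 (95%).
3. **SAP 5.2, item 1.** State that a family-history interaction would be a hypothesis for further research, in line with Protocol 10.4.2.

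The cost is SAP wording and two table columns, with no new data and no change to sample size. The downside is that fewer subgroup statements can be made, and the wide intervals will show how little the trial can say about effect modification.

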5.6. NIH-required Subgroup Analyses

Subgroup analyses by baby's sex, race, and ethnicity will be conducted similarly to the subgroup analyses above, using the full ITT dataset with provider-diagnosed AD as the outcome (which is the study's primary outcome). A regression model with main effects and interactions with intervention assignment and other study design variables will be used to generate estimates.

We will report the numbers of participants with and without AD by 12/24 months in the intervention and usual care arms in each subgroup; the treatment effect (RR) using the group with the lowest-risk group as the reference category; interaction effects with 95% confidence intervals. Some groups defined by race may be very small for statistical inference. In follow-up analyses, we will investigate the possibility that differences in treatment effects, if any, are confounded by other factors, e.g. climate or frequency of emollient use, if these are found to be associated with the primary outcome.

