2.3. Sample Size and Recruitment Duration

1,250 parent/infant dyads (625 per arm) will be enrolled from 25 community-based family medicine and pediatric practices in four states (Oregon, Colorado, Wisconsin, and North Carolina). All parents/legal guardians, including males and females 18 years of age and older who meet inclusion/exclusion criteria are eligible for study participation. Recruitment is expected to take place over the course of 31 months; the time from start of recruitment until final two-year follow-up on all subjects is five years.

Power for Aim 1. For the purpose of the primary analysis, we include a sufficient number of babies in a 1:1 ratio for the two study arms to provide an overall type I error rate of 0.05 and 80% power to detect a 30% relative reduction in cumulative incidence of AD by two years of age (RR=0.7). In our planning grant, we determined the baseline cumulative incidence of AD in this age group and target clinics at 24%, which is consistent with recent population-based 2-year prevalence in the U.K.¹. Because our trials in high-risk populations of daily vs no emollient have shown reductions of 50%, we assume a more conservative 30% reduction to 16.8%. Using a test of two proportions, a total of 982 babies (491 per arm) are required to detect this difference. Allowing for an approximate 20%

¹ The screening questionnaire includes the question "Has at least one of your baby's blood-related PARENTS, BROTHERS OR SISTERS ever been diagnosed with asthma, eczema (atopic dermatitis) or hay fever (seasonal allergies)?" Strata are split at "Yes" responses vs. "No, or don't know."

loss to follow-up, we plan to enroll 1,250 babies (625 per arm). Sample size calculations were performed using Stata/IC version 16.1.

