Power for Aim 2. To determine our power to detect significant interactions, we generated plausible 2x2 tables of risk factors (RFs) and AD for each treatment group that would yield absolute differences in the treatment effect of 0.2, 0.3, and 0.4, taking into consideration the study sample size, overall projected AD and treatment effect, previously published risk of AD for the RF, and prevalence of the RF. We simulated 500 replicates of each scenario using the binomial probabilities from the 2x2 tables and tested for significance of the interaction in a log-binomial (relative risk) model as described below. The power estimates in Table 1 are the proportion of simulated datasets in which the null hypothesis was appropriately rejected.

Table 1. Power to detect plausible interactions in exploratory analyses.

Risk factor (RF)	AD risk	Prev-alence	Tx effect if RF+	Tx effect if RF-	Tx effect DIFF	Power at $\alpha=0.1$
Family history of atopy	2.0	0.50	0.63	0.83	-0.20	0.48
			0.60	0.90	-0.30	0.56
			0.57	0.97	-0.40	0.64
High humidity	0.8	0.44	0.82	0.62	0.20	0.40
			0.89	0.58	0.30	0.52
			0.95	0.54	0.40	0.65
Cat owner	1.0	0.30	0.84	0.64	0.20	0.36
			0.91	0.61	0.30	0.48
			0.98	0.58	0.40	0.60
Dog owner	0.7	0.37	0.84	0.64	0.20	0.36
			0.91	0.61	0.30	0.46
			0.98	0.58	0.40	0.59

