3.4. Adherence

Participants in the intervention arm receive instructions to apply emollient daily, while those in the control arm are asked to refrain from emollient use. Frequency of emollient use, measured in days per week, is assessed for participants in both arms at each of the quarterly contacts from when the child is 3 months old to 24 months old. Participants are reminded of instructions per treatment arm at each quarterly and annual contact. Frequency of emollient use will be analysed as described in section 5 below.

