			Baths/week	Count (0-7+)	p%(x/n) n, mean, SD, Median, min, max
			Prior emollient use	Binary(Y/N)	p%(x/n)
			Prior emollient type	Categorical	p%(x/n)
			Prior emollient brand	Descriptive	p%(x/n)
Emollient Choices	Treatment Group	Baseline 24m or last refill	Prior emollient use per week	Count (0-7+)	p%(x/n) n, mean, SD, Median, min, max
			Gender	Binary(M/F)	p%(x/n)
			Ethnicity	Binary(Hispanic)	p%(x/n)
			Race	Categorical	p%(x/n)
			Education level	Categorical	p%(x/n)
			Emollient choice-baseline	Categorical	p%(x/n)
			Emollient choice-end of study	Categorical	p%(x/n)
			Switched from baseline	Binary(Y/N)	p%(x/n)

Table Title	Population	Time Point(s)	Endpoint	Endpoint Type	Summary Statistics by Treatment Assignment
Cumulative incidence of AD	ITT	24m	Primary outcome: Provider diagnosis of AD in patient chart	Binary(Y/N)	Relative risk(RR) for cumulative incidence
	ITT	12m,24m	Provider diagnosis of AD in patient chart at age 1 year and age 2 years	Binary(Y/N)	RR
	Complete case	12m,24m	Provider diagnosis of AD in patient chart (complete case)	Binary(Y/N)	RR
	ITT	12m,24m	Cumulative incidence of AD by parental report of provider diagnosis	Binary(Y/N)	RR
	ITT	12m,24m	Cumulative incidence of AD by parental report of Children's Eczema Questionnaire	Binary(Y/N)	RR
Age of onset of AD	ITT	All time points	Age of onset by chart review, parent report	Time to event	Kaplan-Meier
Skin Problems	ITT	12m,24m	Dry Skin	Binary(Y/N)	p%(x/n)
			Diagnosed eczema	Binary(Y/N)	p%(x/n)
			Red rash	Binary(Y/N)	p%(x/n)
			Itching	Binary(Y/N)	p%(x/n)
			Areas of rash	Categorical	p%(x/n)
Skin infections	ITT	12m,24m	Presence/absence at any time	Binary(Y/N)	p%(x/n)
			Type	Categorical	p%(x/n)
Rash treatment	AD population	12m,24m	Rash treatment Y/N	Binary(Y/N)	p%(x/n)
			Prescription treatment Y/N	Binary(Y/N)	p%(x/n)
			OTC treatment Y/N	Binary(Y/N)	p%(x/n)
			Specific type	Categorical	p%(x/n)
Skin care	ITT	12m,24m	Baths/week	Count(0-7)	p%(x/n) n, mean, SD, Median, min, max
			>2 baths/week	Binary(Y/N)	p%(x/n)
		12m,24m	>1 bath/week	Binary(Y/N)	p%(x/n)
		All time points before AD diagnosis, if applicable	Frequent emollient user: Report 3 or more days per week at majority of follow-up points	Binary(Y/N)	p%(x/n)
		Q3 months	Moisturizer use Y/N	Binary(Y/N)	p%(x/n)
			Emollient use days/week	Count(0-7)	n, mean, SD, Median, min, max
			Emollient type	Categorical	p%(x/n)
			Which emollients	Categorical	p%(x/n)

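### SAP 5.6 follows up a race or ethnicity difference in effect only for factors associated with AD, a condition that does not identify what makes such a difference spurious on the RR scale, and one of its two examples is a post-randomisation variable

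*SAP*

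**What the plan says.** SAP 5.6 fits arm-by-subgroup models for sex, race and ethnicity, and reports RRs and interaction effects with 95% confidence intervals. Follow-up analyses then examine whether any differences in effect "are confounded by other factors, e.g. climate or frequency of emollient use, if these are found to be associated with the primary outcome". The section names no test, arm, threshold or model for that condition.

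Other places that bear on it:

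- **Climate as a modifier.** SAP 5.2, item 2, cites a risk ratio of 0.8 for AD in the most humid areas and adds: "If emollient prevents AD by preserving the skin barrier, then the treatment effect should be greatest in low-humidity areas". Humidity is assigned from the clinic's locality.
- **Assumed size.** SAP 2.3 built its Table 1 scenarios to give "absolute differences in the treatment effect of 0.2, 0.3, and 0.4".
- **Follow-up emollient use.** By SAP 3.4 its frequency "is assessed for participants in both arms at each of the quarterly contacts", that is, after randomisation. SAP 5.7 plans to read it as lying on the causal pathway from arm to AD.
- **Baseline emollient use.** SAP Table 4 lists "Prior emollient use per week" with the baseline skin-care variables. Protocol 6.1 has the enrolment questionnaire, which covers skin care practices, completed before randomisation.

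**The concern.** The condition in 5.6 suits confounding of a main effect: a common cause of exposure and outcome. The quantity at issue here is an arm-by-race interaction. Arm is randomised, so the ratio of RRs between two race groups is distorted by a factor that (a) changes the arm effect and (b) differs in distribution between the groups. A factor can do both and show no association with AD once the arms are pooled.

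Climate, the SAP's own example, is a case where this is likely. Humidity is expected to lower AD risk and also to weaken the benefit of emollient. Pooled over arms, the two tendencies offset each other. The stronger the modification in Table 1, the less there is for an association screen to find. The clinic random intercept in Equation 1 does not help, because it shifts both arms alike.

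The second example has a different problem. Follow-up emollient frequency is a consequence of assignment. In controls it may also be a consequence of emerging skin trouble, since Protocol 3.3.2 allows emollient if dry skin develops. Conditioning on it does not remove confounding.

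At stake is how a race or ethnicity difference is interpreted. SAP 5.2 predicts a weaker effect in African American infants, and SAP 5.5 puts magnitude above p values. A moderate gap produced by climate could be read as a race effect.

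**Working it through.** **Inputs.** SAP 2.3 gives "overall type I error rate of 0.05 and 80% power to detect a 30% relative reduction in cumulative incidence of AD", and "we determined the baseline cumulative incidence of AD in this age group and target clinics at 24" per cent. SAP 3.1 says: "All tests will be two-tailed". Table 1 gives high humidity an AD risk ratio of 0.8 and a prevalence of 0.44, with arm RRs (humid/dry) of 0.82/0.62, 0.89/0.58 and 0.95/0.54.

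**Step 1: the plan's sample size.** For 24% against 16.8%, two-sided 0.05, 80% power and no continuity correction:

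n = [1.96√(2 × 0.204 × 0.796) + 0.8416√(0.24 × 0.76 + 0.168 × 0.832)]² / 0.072² = (1.117 + 0.478)² / 0.005184 ≈ 491 per arm, or 982 in total, as stated.

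**Step 2: what the 0.8 means.** If it is the control-arm ratio, the overall arm RR is (0.56 × RR_dry + 0.44 × 0.8 × RR_humid) / (0.56 + 0.44 × 0.8). The three rows return 0.697, 0.700 and 0.698, against the planned 0.70. If it is the arm-pooled ratio, they return 0.692, 0.687 and 0.676. The control-arm reading fits better.

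**Step 3: climate–AD association with arms pooled.** Control risks are 0.24/0.912 = 0.263 (dry) and 0.8 × 0.263 = 0.211 (humid). With 1:1 allocation the pooled climate RR is 0.8 × (1 + RR_humid)/(1 + RR_dry). Pass rates below are for a two-sided two-proportion test of climate against AD at N=982.

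| Arm RR humid/dry | Pooled risk dry, humid | Pooled climate RR | Pass at 0.05 | Pass at 0.10 |
|---|---|---|---|---|
| 0.82/0.62 | 0.213, 0.192 | 0.90 | 13.1% | 21.4% |
| 0.89/0.58 | 0.208, 0.199 | 0.96 | 6.3% | 12.0% |
| 0.95/0.54 | 0.203, 0.205 | 1.01 | 5.1% | 10.2% |

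Unpooled variance moves the first row at 0.10 to 21.6%. At N=1,250 the rates are 15.4%, 6.7% and 5.2% at 0.05, and 24.4%, 12.5% and 10.2% at 0.10. In the third row the screen passes climate at about its false-positive rate.

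**Step 4: other readings** (N=982 to 1,250).

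- Test in controls only: 27 to 33% at 0.05, 39 to 45% at 0.10.
- 0.8 read as arm-pooled: 40 to 49% at 0.05, 53 to 62% at 0.10, ignoring clinic clustering. With an assumed ICC of 0.01 to 0.05 and 25 to 45 clinics (N=1,250), these become 18 to 41% and 28 to 53%.

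**Step 5: the difference climate alone can create.** Suppose race does not modify the effect and a group has humid share h. Its RR is [(1−h) × RR_dry + 0.8h × RR_humid] / [(1−h) + 0.8h]. For the third row:

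- h = 0.80: (0.108 + 0.608)/0.84 = 0.852
- h = 0.35: (0.351 + 0.266)/0.93 = 0.663

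The ratio is 1.28. The shares are assumptions; the range is:

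| Humid shares | Row 1 | Row 2 | Row 3 |
|---|---|---|---|
| 60% / 40% | 1.06 | 1.09 | 1.12 |
| 70% / 30% | 1.12 | 1.19 | 1.25 |
| 80% / 35% | 1.14 | 1.21 | 1.28 |
| 90% / 30% | 1.19 | 1.29 | 1.40 |

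Within a climate stratum the two groups share one RR by construction, so a model with an arm-by-climate term returns a ratio of 1.

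**Step 6: would an interaction screen do?** Table 1 gives power of 0.40, 0.52 and 0.65 for climate by arm at 0.10. Screening on that test would still miss climate in 60%, 48% and 35% of trials. That favours having no significance screen.

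**The case against.** Several points on the other side stand.

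- **The rule is not spelled out.** 5.6 names no test. If association were judged by magnitude, or from the control-arm coefficient of an interaction model, a climate ratio of 0.8 might well be noticed. The 5 to 13% belongs to one reading. A reader might infer that climate would fail under any reading; Step 4 shows otherwise.
- **The adjustment is not spelled out either.** A reader might infer that 5.6 plans to add only a main effect of the factor, which would leave the spurious ratio in place. The text does not say so; the method is unspecified.
- **Climate is analysed elsewhere.** SAP 5.2 and 5.5 pre-specify climate by arm, and Table 5 gives it rows and an interaction p value. A reader might infer that a race difference would be reported as unexplained by climate. The documents do not say that; a factor failing the condition would simply not be pursued under 5.6.
- **Scale matters.** 5.5 also uses risk differences. With a constant RR of 0.7, the risk difference is −0.079 in dry areas (0.3 × 0.263) and −0.063 in humid areas (0.3 × 0.211), so association with AD is relevant there. The criticism is confined to the RR scale.
- **Sex is not affected.** Infant sex should be nearly unrelated to clinic climate.
- **Race by climate is unknown.** Four states make imbalance plausible, but no table gives it, and its direction could mask a difference as well as create one.
- **Differing emollient use is a fair question.** Asking whether it explains heterogeneity is legitimate as a question of mechanism. A reader might infer that adjusting for it will create a race difference; that depends wholly on assumed dry-skin rates and usage patterns, so no size is claimed here.

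**Conclusion.** The point holds for race and ethnicity, on the RR scale. The entry condition in 5.6 tests neither of the two properties that matter. On the better-fitting reading of the SAP's own climate scenarios, an arm-pooled significance screen would overlook climate in roughly 78 to 95% of trials at N=982. On the readings more favourable to the plan it would still overlook it in 38 to 73%. The spurious ratio of RRs is about 1.06 to 1.40, conditional on the Table 1 effects and the assumed humid shares.

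Listing follow-up emollient frequency as a possible confounder is inconsistent with 5.7, whatever the numbers.

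The consequence is limited: these are follow-up analyses to NIH-required subgroup comparisons, the primary result is untouched, and climate by arm is reported separately. This is an inexpensive improvement to the plan and no threat to the trial's main conclusion.

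**What to change.** In SAP 5.6, delete the closing condition on association with the primary outcome and replace the follow-up sentence with text to this effect:

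- For any race or ethnicity difference in effect, refit the model adding the main effect and the arm-by-factor term for each pre-listed baseline factor: climate, family history, pets, and prior emollient use per week. Family history is already a main effect in Equation 1, so only its interaction is new.
- Enter one factor at a time, whether or not it is associated with AD. SAP 5.3 already anticipates convergence problems; use its robust-variance Poisson fallback if needed.
- Report the subgroup interaction with its 95% CI before and after each addition.
- Do not adjust these models for follow-up emollient frequency. Tabulate it by arm and subgroup as a possible mechanism.

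The cost is SAP wording, a few more exploratory models and a somewhat wider CI on the adjusted interaction. No new data are needed. The change should be made before the arm labels are revealed.
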